was in critical situation, uncooperative, or with uncontrolled movement, the anesthesiologist would choose the intubated Sev-GA instead of the scheduled randomization. However, if patient is cooperative and not critical, the patient would be randomly assigned according to the randomization list created with the use of computer-generated, permuted-block sequences. Only the anesthesiologist and physicians involved in EVT are aware of the anesthesia assignment. On the contrary, patients, personnel who collect data, fill out questionnaire and scale measurement, and personnel who assess outcomes are unaware of the group assignments.

The case number is determined according to previous studies. [Ellard et al., 2014; Katznelson et al., 2009; Matsuzono et al., 2020] Under the null hypothesis of there is no mean difference between two groups and no patients lost follow-up. The type I error is set as 0.05 with power of 0.8. A total of 298 patients is required to detect a difference of 12.8% in POCD incidence in acute ischemic stroke patients receiving EVT therapy within 7 days after stroke. Considering the potential 10% attrition rate, a sample size of 328 participants will be recruited into the present clinical trial.

General anesthesia protocol

American Society of Anesthesiologists standard monitors (including pulse oximeter, ECG, and non-invasive blood pressure), invasive arterial blood pressure monitoring, end-tidal agent monitor (including CO₂ and anesthetic concentrations), hypnotic level monitor (either BIS or PSI), and cerebral oximeter using near-infrared spectroscopy are applied to all patients peri-procedurally.

Non-intubated TIVA-propofol group:

With the application of Optiflow nasal high flow set at a flow rate of 20 L/min and 60% FiO₂, total intravenous anesthesia is induced with target-controlled infusion of propofol (effect site (Ce) concentration around 1.5-2 μ g/ml) and remifentanyl (Ce value around 1.0-1.5 ng/ml), and adjusted as required.

Intubated Sev-GA group:

After preoxygenation for 3 minutes with 100% oxygen, anesthesia is induced with intravenous injection of propofol (1.5-2 mg/kg), remifentanyl infusion (Ce value around 1-1.5 ng/kg), and cisatracurium (0.15-0.2 mg/kg), and followed by endotracheal intubation. General anesthesia is maintained with cisatracurium (0.03 mg/kg every 45-50 min), remifentanyl (Ce value around 1-1.5 ng/kg) and sevoflurane inhalation. Sevoflurane concentration will be adjusted to keep BIS value within the range of 40-60. Mechanical ventilation will be processed at volume-controlled mode with fraction of inspired oxygen (FiO₂) 60%, tidal volume 6 ml/kg, and respiratory rate 9-12/min

to keep normocapnia and avoid desaturation during the EVT procedure.

Peri-EVT procedural anesthetic monitoring

1. Standard monitoring: continuous ECG, non-invasive blood pressure (NIBP), pulse oximeter (SpO₂)
2. Invasive arterial blood pressure (ABP)
3. Anesthetic agent monitor: to monitor sevoflurane concentration
4. Cerebral oximeter (ScO₂): for regional brain oxygenation monitor
5. End-tidal CO₂ (ETCO₂) monitor
6. Processed electroencephalogram (EEG) monitoring: either with Medtronic BIS™ brain monitoring system with bispectral index (BIS) or Masimo SedLine Brain function monitoring with Patient State Index (PSI)

Physiologic target during peri-EVT procedure

1. Propofol target effect-site concentration (Ce): 1.5 ~ 2.0 μ g/ml.
2. Remifentanyl Ce: 1.0 ~ 1.5 ng/ml
3. Partial pressure of arterial blood CO₂ (PaCO₂): kept around 30-40 mmHg
4. ETCO₂: kept around 35-45 mmHg
5. Target-controlled sedation level: PSI maintained between 25 and 50 or BIS maintained between 40 and 60 by adjusting the infusion rate of propofol or the inhaled concentration of sevoflurane
6. Systolic blood pressure (target-controlled): before completion of thrombectomy (110-180 mmHg), and after completion of thrombectomy (110 -140 mmHg).

Post-procedural care

After completion of the EVT procedure, patient will be transferred to the Stroke Care Unit for post-procedural intensive care. The endotracheal tube will be removed once weaning from mechanical ventilation, ability to spontaneous respiration, and recovery of both muscle power and respiratory mechanics.

Outcomes:

Cognitive function and delirium evaluation

Cognitive functions (including delirium) will be assessed pre-procedure (baseline) and emergency department (before EVT), on days 1 and 7 after EVT procedure, using the confusion assessment method (CAM).

Neurological functional assessment

National Institute of Health Stroke Scale (NIHSS) and modified Rankin scale (mRS) will be assessed before (baseline but after stroke) and after EVT on days 1 and 7 after procedure up to 3 months follow-up.

Data collection and analysis

The primary outcome is to compare the incidence and severity of postoperative delirium between intubated GA-sevoflurane and non-intubated TIVA-propofol, which is assessed using CAM. The secondary outcomes are neurological and clinical outcomes by assessing the NIHSS and mRS, and activity of daily living. All analyses are based on the intention-to-treat principle. The normally distributed data will be expressed as mean \pm SD, while non-normally distributed data will be presented as median and interquartile ranges (IQR). Binary outcomes will be analyzed with logistic regression. The Chi-Square test is used to compare categorical data. The Mann-Whitney test and Kruskal-Wallis test are used to compare non-normally distributed data within the trial. Modified Rankin score is analyzed with an ordinal logistic regression. Safety outcomes are assessed with Chi-Square test for categorical variables and Student's t test for continuous variables. *P* values less than 0.05 are considered statistically significant. All data analysis will be performed using the Statistical Package for the Social Sciences (SPSS) version 17.0 for Windows (SPSS Inc., Chicago, IL, USA).

Questionnaire

1. Modified Rankin Scale: assessed before procedure and the day at discharge, respectively.

Score	Degree of disability or dependence in the daily activities
0	No symptoms
1	No significant disability: able to carry out all usual activities, despite some symptoms
2	Slight disability: able to look after own affairs without assistance, but unable to carry out all previous activities
3	Moderate disability: requires some help, but able to walk unassisted
4	Moderately severe disability: unable to attend to own bodily needs without assistance, and unable to walk unassisted
5	Severe disability: requires constant nursing care and attention, bedridden, incontinent
6	Dead

2. National Institutes of Health Stroke Scale (NIHSS): assessed before procedure and day 1 after EVT, and the day at discharge, respectively.

Time point	Before EVT	D1 after EVT	Day at discharge
------------	---------------	-----------------	---------------------

1a. Level of consciousness, Responsiveness	0: Alert; responsive 1: Not alert; Verbally arousable or aroused by minor stimulation to obey, answer, or respond 2: Not alert; Only responsive to repeated or strong and painful stimuli 3: Totally unresponsive; Responds only with reflexes or is areflexic			
1b. Level of consciousness, Questions	0: Correctly answers both questions 1: Correctly answers one question 2: Does not correctly answer either question			
1c. Level of consciousness, Commands	0: Correctly performs both tasks 1: Correctly performs 1 task 2: Does not correctly perform either task			
3. Horizontal Eye Movement	0: Normal; Able to follow pen or finger to both sides 1: Partial gaze palsy; gaze is abnormal in one or both eyes, but gaze is not totally paralyzed. Patient can gaze towards hemisphere of infarct, but cannot go past midline 2: Total gaze paresis; gaze is fixed to one side			
4. Visual field test	0: No vision loss 1: Partial hemianopia or complete quadrantanopia; patient recognizes no visual stimulus in one specific quadrant 2: Complete hemianopia; patient recognizes no visual stimulus in one half of the visual field 3: Bilateral Blindness, including blindness from any cause			
5. Facial palsy	0: Normal and symmetrical movement 1: Minor paralysis; function is less than clearly normal, such as flattened nasolabial fold or minor asymmetry in smile 2: Partial paralysis; particularly paralysis in lower face			

	3: Complete facial Hemiparesis, total paralysis in upper and lower portions of one face side			
6. Motor Arm	0: No arm drift; the arm remains in the initial position for the full 10 seconds 1: Drift; the arm drifts to an intermediate position prior to the end of the full 10 seconds, but not at any point relies on a support 2: Limited effort against gravity; the arm is able to obtain the starting position, but drifts down from the initial position to a physical support prior to the end of the 10 seconds 3: No effort against gravity; the arm falls immediately after being helped to the initial position, however the patient is able to move the arm in some form (e.g. shoulder shrug) 4: No movement; patient has no ability to enact voluntary movement in this arm	Left (5a)		
		Right (5b)		
6. Motor Leg	0: No leg drift; the leg remains in the initial	Left (6a)		

	
position for the full 5 seconds
 
1: Drift; the leg drifts to an intermediate position prior to the end of the full 5 seconds, but at no point touches the bed for support
 
2: Limited effort against gravity; the leg is able to obtain the starting position, but drifts down from the initial position to physical support prior to the end of the 5 seconds
 
3: No effort against gravity; the leg falls immediately after being helped to the initial position, however, the patient is able to move the leg in some form (e.g. hip flex)
 
4: No movement; patient has no ability to enact voluntary movement in this leg
	
Right
 
(6b)
			

7. Limb ataxia
	
0: Normal coordination; smooth and accurate movement
 
1: Ataxia present in 1 limb; rigid and inaccurate movement in one limb
 
2: Ataxia present in 2 or more limbs: rigid and inaccurate movement in both limbs on one side
				

8. Sensory	0: No evidence of sensory loss 1: Mild-to-Moderate sensory loss; patient feels the pinprick, however he or she feels as if it is duller on one side 2: Severe to total sensory loss on one side; patient is not aware he or she is being touched in all unilateral extremities			
9. Language	0: Normal; no obvious speech deficit 1: Mild-to-moderate aphasia; detectable loss in fluency, however, the examiner should still be able to extract information from patient's speech 2: Severe aphasia; all speech is fragmented, and examiner is unable to extract the figure's content from the patient's speech. 3: Unable to speak or understand speech			
10. Speech	0: Normal; clear and smooth speech 1: Mild-to-moderate dysarthria; some slurring of speech, however the patient can be understood 2: Severe dysarthria; speech is so slurred that he or she cannot be understood, or patients that cannot produce any speech			
11. Extinction and Inattention	0: Normal; patient correctly answers all questions 1: Inattention on one side in one modality; visual, tactile, auditory, or spatial 2: Hemi-inattention; does not recognize stimuli in more than one modality on the same side			
Scores (0-42)				

6. Confusion Assessment Method (CAM): assessed before procedure and day 1 and 7 after EVT, and the day at discharge, respectively.

Confusion Assessment Method (CAM)	Date of Assessment	Before EVT	D1 after EVT	D7 after EVT	Day at discharge
-----------------------------------	--------------------	------------	--------------	--------------	------------------

Diagnostic Algorithm	Time of Assessment				
		Yes or No	Yes or No	Yes or No	Yes or No
1. Acute onset and fluctuating course? (Acute change in mental status from baseline, fluctuating behavior through the day)					
2. Inattention? (Difficulty focusing attention, easily distracted, difficulty keeping track of what is being said)					
3. Disorganized thinking? (disorganized or incoherent thinking, rambling or irrelevant conversation, unclear or illogical flow of ideas)					
4. Altered level of consciousness? (This feature is shown by any answer other than "alert", including: hyper-alert, lethargic, stupor, or coma)					
The diagnosis of Delirium by CAM requires the presence of features 1 and 2 AND EITHER 3 or 4					
Delirium detected		Yes No (Circle)	Yes No (Circle)	Yes No (Circle)	Yes No (Circle)

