Delirium is characterized by disturbances of attention and cognition that cause functional decline and complications. The predisposing factors of delirium are age, male gender, systemic or metabolic disorders, dementia, and stroke. [Alvarez-Perez and Paiva, 2017; Caeiro et al., 2004] Postoperative neurocognitive disorders including postoperative dementia (POD) and postoperative cognitive dysfunction (POCD) not only affect cognitive function but also increase the risk for significant complications such as dementia and death. [Avelino-Silva et al., 2017; Rudolph and Marcantonio, 2011] Patient's characteristics including carotid and intracranial arterial

atherosclerosis, prior stroke and transient ischemic attack, intraoperative factors such as general anesthesia and inhaled anesthetics, and postoperative factors might precipitate to the development of POD and POCD with prolonged in-hospital stay and costs. [Ravi et al., 2019; Rutdolph and Marcantonio, 2011] The incidence of POCD/POD has been estimated to develop in 46% of patients undergoing cardiac surgery, with delirium lasting 1 to 2 days in 65% of these patients and 3 or more days in 35%; 9.1% of patients undergoing fast-track hip and knee surgery at 1 to 2 weeks and 8.0% at 3 months; 19.4%-22% in patients undergoing vascular surgery. [Ellard et al., 2014; Krenk et al., 2014; Saczynski et al., 2012; Katznelson et al., 2009]

Cognitive dysfunction after ischemic stroke

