Ischemic stroke could injure the brain with both neurological dysfunction (including cognitive impairment) and physical disability in patients. It has been shown in the Framingham study that hemiparesis was most common neurological deficit (50%), followed by the cognitive deficits (46.2%), after ischemic brain stroke in elderly. [Kelly-Hayes et al., 2003] In addition, 22.2% to 39.6% patients with ischemic stroke were significantly more disabled from all domains including dependence on activity of daily living, poor health, incontinence, depression, social disability, and need institutionalization. [Kelly-Hayes et al., 2003] In MEDIAS (the Management Effort for Delirium and Insomnia in Acute Ischemic Stroke) study, delirium occurred in 25.8% of acute ischemic stroke patients (i.e., within 7 days after stroke onset) and these delirium patients were older and had significantly worse modified Rankin scale (mRS) scores both at discharge and 1 year after stroke onset. [Matsuzono et al., 2020] Furthermore, these acute ischemic stroke patients with delirium received delirium management including physical restraint alone (45.3%), combined physical restraint and major tranquilizers (36.8%), and major tranquilizers alone (17.8%). The authors raised the concern that physical restraint may be required to ensure patient safety but inversely have potential harmful consequences including death in these acute ischemic stroke patients with delirium. [Matsuzono et al., 2020]

Target-monitored GA to reduce the risk of intraoperative awareness and unfavorable hypotension

The goals of GA are to provide unconsciousness, amnesia, analgesia, and blunting of sympathetic stress responses; however, the incidence of intraoperative awareness during general anesthesia has been estimated to around 0.1-0.2% among general anesthesia. [Myles et al., 2004] Intraoperative awareness can cause significant psychological trauma to the patient which results in

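### Severity of delirium is part of the primary outcome, but the plan defines no severity score and no rule for combining it with incidence; the sample size covers incidence only, under the label POCD

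*Combined protocol and SAP*

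**What the plan says.** - **Primary outcome** (Data collection and analysis): "The primary outcome is to compare the incidence and severity of postoperative delirium" between the two anesthetic arms, using CAM. Binary outcomes go to logistic regression. Chi-square and rank tests are listed in general terms, and ordinal logistic regression is named for the modified Rankin score only.
- **Instrument** (Outcomes, and Questionnaire 6): CAM is the only tool named for cognitive function, delirium included. The schedule reads "Confusion Assessment Method (CAM): assessed before procedure and day 1 and 7 after EVT, and the day at discharge". Each feature is marked yes or no, and "The diagnosis of Delirium by CAM requires the presence of features 1 and 2 AND EITHER 3 or 4". The form has no grade or score.
- **Sample size** (Materials and methods, Subjects): "A total of 298 patients is required to detect a difference of 12.8% in POCD incidence". The type I error is 0.05, the power is 0.8, and the window is worded as "receiving EVT therapy within 7 days after stroke". Neither event rate, the sidedness nor the allocation ratio is given. A 10% attrition allowance takes 298 to 328.
- **Hypothesis and Aim**: both name cognitive dysfunction alongside delirium.
- **Background**: the section on cognitive dysfunction after ischemic stroke reports a 25.8% delirium rate within 7 days of stroke onset. The preceding section pools the two conditions: "The incidence of POCD/POD has been estimated to develop in 46% of patients undergoing cardiac surgery".

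**The concern.** A primary outcome should lead to one defined variable, one comparison and one conclusion. Incidence does: it has an instrument, a diagnostic rule, assessment days and a test. Severity has none of these beyond the general list of tests. Someone would have to choose, after seeing the data, among a feature count, the worst day, the number of positive days or some other summary, and these need not agree. Nor does the plan say whether the trial succeeds if one component favours an arm and the other does not.

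The sample-size sentence adds a second gap. Its 80% power is attached to POCD, which the text never defines separately from CAM delirium. A reader cannot tell from that sentence that the trial is powered for its primary outcome, and a POCD conclusion would rest on delirium data.

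**Working it through.** **1. What CAM can say about severity.** Four yes/no features give 2^4 = 16 patterns. The rule (1 and 2, and either 3 or 4) is met by three of them:

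| Features present | Count | CAM |
|---|---|---|
| 1, 2, 3 | 3 | positive |
| 1, 2, 4 | 3 | positive |
| 1, 2, 3, 4 | 4 | positive |
| 1, 3, 4 | 3 | negative |
| 2, 3, 4 | 3 | negative |

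Among delirious patients a feature count takes only the values 3 and 4. Across all patients, a count of 3 is CAM-positive in two patterns and CAM-negative in the other two. So the count barely grades delirium, and it can contradict the diagnosis.

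**2. Reproducing 298.**

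Inputs from the plan: alpha 0.05, power 0.80, difference 0.128. Input from the background: 25.8% delirium within 7 days of stroke. Assumed: second rate 0.258 − 0.128 = 0.130, two-sided test, 1:1 allocation.

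Formula (pooled under the null), per arm:

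n = [1.960·√(2·p̄(1−p̄)) + 0.842·√(p1(1−p1) + p2(1−p2))]² / (p1−p2)²

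- p̄ = (0.258 + 0.130)/2 = 0.194
- First term: 1.960 × √0.312728 = 1.0961
- Second term: 0.842 × √0.304536 = 0.4644
- n = (1.5605)² / 0.016384 = 2.4352 / 0.016384 = 148.63, so 149 per arm, **298 in total**

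This matches the plan exactly. It is not a unique match. With a 12.8-point gap, 298 also arises at a higher rate of 26.2–26.3% (two-sided, unpooled), 33.5–33.7% (one-sided, pooled) or 23.3% (two-sided, continuity-corrected). It supports the delirium reading without proving it.

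**3. What the calculation leaves out.** It concerns a difference in proportions. No N can be computed for severity, because the plan gives no scale, spread or distribution. As an illustration only: if incidence and severity were two separate primary tests at 0.025 each, the incidence test alone would need 362 evaluable patients under the same rates, and 298 would give about 71% power.

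**4. Attrition (minor).** 298 × 1.10 = 327.8, hence 328. A 10% loss leaves 328 × 0.90 = 295.2, not 298. Under the inferred rates and 1:1, power is 80.1% at 298 and 79.7% at 295. Equal arms are not guaranteed, because critical, uncooperative or uncontrollably moving patients go to sevoflurane outside the randomization. At 295, an assumed 60:40 split gives about 77–79% and an assumed 2:1 split about 73–77%, depending on which arm is larger.

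**The case against.** The strongest reply is that this is mostly wording. Delirium incidence is well specified. The POCD label looks like a slip: the background pools POCD and POD, the 25.8% delirium rate sits under a heading on cognitive dysfunction, and CAM is said to cover cognitive functions in general. Most of this stands, and it is why the label is only a secondary point here.

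A reader might infer that the trial is powered for the wrong endpoint, or that 298 is wrong. The documents do not support that, since 298 follows from the quoted delirium rate. Nor do they show that POCD or severity will go unmeasured. The questionnaires are numbered 1, 2 and 6, and activity of daily living is an outcome with no form shown, so other forms may exist outside the text. A severity form among them is less likely, because the primary outcome is said to be assessed with CAM and that form is printed.

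It is also fair to say that the listed chi-square and rank tests could be applied to a severity score once one existed. What is missing is the variable and the decision rule, not a class of test. Relabelling the sample size would not supply either.

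Finally, one might read the two clocks (7 days from stroke, days 1 and 7 from EVT) as a serious conflict. It is a matter of using one window throughout, and nothing here rests on it.

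**Conclusion.** The concern holds for the primary-outcome definition. Severity is one of two named components, yet the text gives it no score, no assigned analysis and no rule for disagreement with incidence. This should be settled before any outcome data are seen.

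The sample-size label is a lesser, related fault. The power statement should name the primary outcome, but 298 is not shown to be wrong and need not change. That reading rests on the inferred 13.0% rate, a two-sided pooled test and 1:1 allocation, none of which the plan states. The attrition shortfall is about 0.4 percentage points of power under those assumptions, and more if the arms are unequal.

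The conclusions on severity and POCD are limited to the forms in the text.

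**What to change.** 1. **Primary endpoint.** Name one: CAM-positive delirium (yes/no) at the day 1 or day 7 assessment after EVT. Use the same window in the sample-size text.
2. **Severity.** Unless the sponsor confirms a severity instrument among the forms not in the text (questionnaires 3–5), make severity secondary and descriptive, with its scoring rule written before the data are seen.
3. **Sample size.** Replace POCD incidence with incidence of CAM-defined delirium. Print both assumed rates, the sidedness and the allocation ratio once the sponsor confirms them. N is unchanged. The attrition sentence can say that 328 enrolled leaves about 295 after a 10% loss.
4. **Baseline delirium.** The plan does not say how a patient who is CAM-positive before EVT enters an incidence. Adjust the primary logistic regression for the pre-EVT CAM result already collected, and add a supportive repeat that excludes those patients. Quote no power for the repeat, because the documents give no baseline rate.
5. **Hypothesis, Aim and conclusions.** Limit them to delirium unless a separate cognitive instrument is confirmed.

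The new endpoint definition should also state how patients who die or cannot be assessed by day 7 are counted, since the plan gives no rule.

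**Cost.** No new assessment and no change in N, but the primary outcome is amended. Severity is no longer a primary claim, and a separate POCD claim is given up unless an instrument is confirmed.

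### Recruiting 328 does not cover the stated 10% attrition: about 295 patients would remain, against the 298 required

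*Combined protocol and SAP*

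**What the plan says.** The sample-size paragraph is under Materials and methods, Subjects, just before the general anesthesia protocol. It sets the error rates: "The type I error is set as 0.05 with power of 0.8". It gives the number needed: "A total of 298 patients is required to detect a difference of 12.8% in POCD incidence". The sentence before these makes clear that this number assumes complete follow-up: "Under the null hypothesis of there is no mean difference between two groups and no patients lost follow-up". The paragraph then moves to the recruitment target: "Considering the potential 10% attrition rate, a sample size of 328 participants will be recruited into the present clinical trial".

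The inflation formula is not written out. The document does not plan to replace lost patients and makes no other allowance for loss.

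**The concern.** An attrition rate is normally a proportion of the patients enrolled, since that is the group from which patients are lost. To finish with 298 after losing 10% of those recruited, one divides 298 by 0.90. Adding 10% to 298 gives a smaller number, because the loss then applies to the enlarged total. The stated target looks like the second calculation.

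What is at stake is whether the recruitment figure delivers the evaluable number that the plan itself requires. The base calculation appears to have almost no slack above 80% power, so even a small shortfall could take it below the stated level.

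**Working it through.** **Inputs from the sample-size paragraph:** required number 298 (no losses), attrition 10%, recruitment target 328.

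**Reproducing the plan's figure**

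- Multiplying: 298 × (1 + 0.10) = 327.8, rounded up to 328. This matches the plan exactly.

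**Checking it against the stated attrition**

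- Remaining after 10% loss: 328 × (1 − 0.10) = 295.2, about 295. Shortfall: 298 − 295 = 3 patients.
- Attrition that 328 can absorb: (328 − 298) / 328 = 30/328 = 9.1%.
- Target that keeps 298: 298 / (1 − 0.10) = 331.1, rounded up to 332. Check: 332 × 0.90 = 298.8, which covers 298; 331 × 0.90 = 297.9, which does not.
- Difference in recruitment: 332 − 328 = 4 patients, or 4/328 = 1.2%.

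These steps use only 298, 10% and 328. They do not depend on event rates, sidedness, the test or the allocation ratio.

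**Effect on power.** This part needs assumptions, because the paragraph gives a difference of 12.8 points but no event rates.

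- Reference incidence: 25.8%. The background section on cognitive dysfunction after ischemic stroke reports that "delirium occurred in 25.8% of acute ischemic stroke patients (i.e., within 7 days after stroke onset", and the sample-size paragraph cites the same study.
- Other arm: 25.8% − 12.8% = 13.0% (inferred).
- Two-sided test at 0.05, 1:1 allocation, pooled-variance comparison of two proportions, no continuity correction (all assumed).

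The formula per arm is n = [1.960 × √(2p̄(1 − p̄)) + 0.842 × √(p₁(1 − p₁) + p₂(1 − p₂))]² / (p₁ − p₂)², with p̄ = (0.258 + 0.130)/2 = 0.194.

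- √(2 × 0.194 × 0.806) = √0.3127 = 0.5592
- √(0.258 × 0.742 + 0.130 × 0.870) = √0.3045 = 0.5518
- n = (1.0961 + 0.4644)² / 0.128² = 148.6, rounded up to 149 per arm, 298 in total. This matches the plan.

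Power follows from the same formula solved for z = [0.128 × √n − 1.960 × 0.5592] / 0.5518:

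| Evaluable in total | Per arm | Power |
|---|---|---|
| 298 | 149 | 80.1% |
| 295.2 | 147.6 | 79.7% |

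The loss is about 0.4 percentage points.

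**Sensitivity to the formula.** At the same rates, the unpooled formula requires 292 and the arcsine formula 294. With 147.6 per arm they give power of 80.5% and 80.4%. They do not reproduce 298, but by either of them the plan would still reach 80%.

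**The case against.** The strongest reply concerns materiality. The gap is four recruits, and the protocol calls the 10% only potential and gives no source for it. The difference between 9.1% and 10% lies well inside the uncertainty of such a guess, and no analysis or conclusion would change. This is right, and it is why the point is minor.

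The power shortfall is also conditional. It rests on an inferred 13.0% incidence, equal arms and a pooled test, and the unpooled and arcsine formulas keep power just above 80%. Even 79.7% rounds to the protocol's 0.8. This stands too. The firm finding is the shortfall in evaluable patients; the power figure illustrates its size.

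Equal arms are not guaranteed either. The protocol states no allocation ratio, and critical, uncooperative or uncontrollably moving patients go to the sevoflurane arm outside the randomization list. Any per-arm figure here is therefore an assumption. The total of 332 does not depend on it.

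Two other readings would explain 328. The 10% might mean a margin on top of 298, but the text calls it an attrition rate and uses it to pass from a required to a recruited number. Alternatively, a two-sided continuity-corrected calculation at 25.8% versus 13.0% also gives 328. The paragraph attributes the step from 298 to attrition, however, so this looks like coincidence.

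Finally, the paragraph sizes the trial on cognitive dysfunction while the primary outcome is delirium by CAM. If that is revisited, 298 itself may change. The new figure would still need the division by one minus the attrition rate.

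**Conclusion.** The concern holds. As written, 298 required, 10% attrition and 328 recruited are inconsistent: 328 leaves about 295 at 10% attrition, 3 short, and covers 9.1%. This follows from the plan's own three numbers, with attrition read in the usual way as a share of those recruited.

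The consequence is small. Power is 79.7% rather than 80.1% under the assumptions that reproduce 298 (25.8% versus 13.0%, two-sided, equal arms, pooled test), and about 80.4% to 80.5% under two other standard formulas. It is an arithmetic correction and does not threaten the trial.

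**What to change.** Change one sentence in the sample-size paragraph. Any of these makes the figures agree:

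1. Keep 328 and state that it allows for 9.1% attrition while retaining 298 evaluable patients. No extra patients.
2. Keep 328 and 10%, and state that about 295 patients would then be evaluable. If power is quoted (79.7%), give the incidences, test and allocation behind it. No extra patients.
3. Keep 298 and 10%, and raise the target to 332 (166 per arm if allocation is 1:1). Four more patients.

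Either of the first two is enough. Writing out the inflation formula would also let a reader check the step directly.

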Patients undergoing EVT can be managed either with conscious sedation anesthesia in spontaneous breathing or general anesthesia (GA) with volatile anesthetics or total intravenous anesthesia (TIVA). There are debates about the advantages between these anesthetic managements: GA provides muscular paralysis to facilitate intracranial arterial stenting in difficult cases and avoid the possible EVT-related complications, endotracheal intubation to prevent aspiration, and improved patient comfort, while conscious sedation anesthesia shortens the time to intervention (i.e., delay to groin puncture and reperfusion) without delay waiting for anesthesia team and avoids the GA-related detrimental side effects. Furthermore, GA-induced profound decrease in blood pressure and mechanical hyperventilation-produced hypocapnia and cerebral vasoconstriction might worsen the neurological outcomes in the acute ischemic stroke patients which raise concerns not favoring GA for the anesthetic management of EVT. [Takahashi et al., 2014] However, 3 randomized controlled trials including SIESTA (Sedation versus Intubation for Endovascular Stroke Treatment), AnStroke (Anesthesia During Stroke), and GOLIATH (General or Local Anesthesia in Intra Arterial Therapy) revealed no significant difference between GA and conscious sedation in neurological outcome as assessed by post-EVT National Institute of Health Stroke Scale, modified Rankin score, and infarct volume demonstrated on MRI diffusion-weighted imaging study in patients with acute ischemic stroke undergoing EVT, but with higher rates of successful reperfusion and better clinical outcome in general anesthesia group. [Hendén et al., 2017; Schönenberger et al., 2016; Simonsen et al., 2018] Therefore, GA is considered safe for the anesthetic management of EVT procedure.

General anesthesia and postoperative cognitive dysfunction or delirium

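### The PaCO2 target is printed 5 mmHg below the ETCO2 target, the reverse of the usual order, and the plan does not say which one governs

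*Combined protocol and SAP*

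**What the plan says.** In the combined protocol and SAP, the list headed "Physiologic target during peri-EVT procedure" gives two CO2 targets as consecutive items. PaCO2 is to be "kept around 30-40 mmHg" (item 3) and ETCO2 "kept around 35-45 mmHg" (item 4). Neither item names an arm.

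Three other places bear on how these lines would be used:

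- Under General anesthesia protocol, end-tidal CO2 monitoring and "invasive arterial blood pressure monitoring" apply to all patients. The separate list of peri-procedural monitoring includes ETCO2 but no blood gas.
- In the paragraph on the intubated Sev-GA group, ventilation is set "to keep normocapnia and avoid desaturation during the EVT procedure". No CO2 range is attached to that instruction.
- The background section Anesthesia for EVT reports the worry that "mechanical hyperventilation-produced hypocapnia and cerebral vasoconstriction might worsen the neurological outcomes in the acute ischemic stroke patients".

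No text states an expected difference between arterial and end-tidal CO2, says when arterial gas is sampled, or ranks one target above the other.

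**The concern.** Two written targets for closely linked measurements should be compatible over most of their range. Here the arterial range sits below the end-tidal range, whereas arterial CO2 is normally equal to or somewhat higher than end-tidal CO2. The anesthesiologist can therefore be on target by one line and off target by the other, with no rule for which to follow.

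The part of the conflict that matters most is the lower end of the arterial line. A PaCO2 of 30-35 mmHg satisfies item 3. If normocapnia is taken as 35-45 mmHg, that is low arterial CO2. The Sev-GA paragraph asks staff to avoid this state, and the background names it as a possible cause of worse neurological outcome. What is at stake is clear and safe conduct of the anesthetic.

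**Working it through.** **Inputs.** From the target list: PaCO2 30-40 mmHg and ETCO2 35-45 mmHg. Let g = PaCO2 - ETCO2. The documents do not give g, so it is an assumption shown over a range. Under the usual ordering, g is 0 or more.

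**Offset.** Lower bounds: 35 - 30 = 5. Upper bounds: 45 - 40 = 5. The arterial range is 5 mmHg lower throughout.

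**Values that meet both printed targets.** ETCO2 between 35 and 45 means PaCO2 between 35 + g and 45 + g. Both lines are met when

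max(30, 35 + g) ≤ PaCO2 ≤ min(40, 45 + g).

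| Assumed g (mmHg) | PaCO2 meeting both | Matching ETCO2 | Width (mmHg) |
|---|---|---|---|
| -5 | 30-40 | 35-45 | 10 |
| -2 | 33-40 | 35-42 | 7 |
| 0 | 35-40 | 35-40 | 5 |
| 2 | 37-40 | 35-38 | 3 |
| 5 | 40 only | 35 only | 0 |
| 6 | none (41 > 40) | none | none |

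The printed ranges agree in full only at g = -5, with end-tidal above arterial. For g of 0 or more the joint band is at most 5 of the 10 mmHg in either range.

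**Transposition check.** Swap the ranges (PaCO2 35-45, ETCO2 30-40). The joint band runs from max(35, 30 + g) to min(45, 40 + g):

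- g = 0: 35-40 (width 5)
- g = 2: 35-42 (width 7)
- g = 5: 35-45 (width 10, full agreement)

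The swapped pair agrees best at a positive gap. That fits a transposition but does not prove one.

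**Low arterial CO2.** If PaCO2 is below 35 and g is 0 or more, then ETCO2 = PaCO2 - g is also below 35 and misses item 4. So PaCO2 of 30 up to 35 is on target by item 3 and off target by item 4 unless end-tidal exceeds arterial. A team that meets both lines stays at PaCO2 35-40.

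**Replacement pair.** With PaCO2 35-45 and ETCO2 35-40, an on-target ETCO2 gives PaCO2 from 35 + g to 40 + g:

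- g = 0: 35-40
- g = 2: 37-42
- g = 5: 40-45

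Every on-target end-tidal value therefore gives an on-target arterial value for any g from 0 to 5. At g = 6 the top of the band would be 46, which is 1 mmHg over.

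**The case against.** The strongest reply is that the two lines do not flatly contradict each other. Both are worded as approximate, and they overlap. They can be met together at every assumed gap from 0 to 5 mmHg. ETCO2 is the only CO2 measurement on the monitoring list, so in practice staff will follow the end-tidal line, which with the usual ordering keeps PaCO2 at 35 or above. In the Sev-GA arm the normocapnia instruction pushes the same way. The list also mixes in arm-specific items such as the propofol concentration, so applying both CO2 lines to every patient is an inference, though a fair one given the common monitoring.

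Most of this stands and limits the weight of the point. It does not explain a uniform 5 mmHg shift in the unusual direction, and it supplies no rule for which line governs.

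A reader might infer three stronger things, none of which the documents support:

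- *The plan directs hyperventilation.* It does not. Low arterial CO2 arises mainly if the PaCO2 line is followed alone.
- *In the non-intubated arm no value can meet both targets.* A reader might argue that end-tidal readings fall short of the true value with "Optiflow nasal high flow set at a flow rate of 20 L/min", so that the apparent gap passes 5 mmHg. The documents say nothing about reading error under nasal high flow and give no gap of any size.
- *The mismatch biases the comparison of the arms.* Both lines stand in one common list, and nothing in the text links them to a difference between the arms in delirium or neurological outcome.

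**Conclusion.** The point holds as a minor conduct and safety correction. The documents alone establish the 5 mmHg offset, the common list and the absence of a governing rule. Two further steps rest on stated assumptions: that arterial CO2 is at or above end-tidal CO2, and that normocapnia means 35-45 mmHg. Under the first, the band meeting both targets is at most 5 mmHg wide, shrinks to the single value 40 at a gap of 5 and is empty beyond that. Under the second, the 30-35 part of the arterial line, read alone, conflicts with the Sev-GA instruction and with the background concern about hypocapnia. Transposition is a plausible explanation only. The sample size, endpoints and analysis are unaffected.

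**What to change.** Edit the two target lines and add one sentence. For example:

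- PaCO2: 35-45 mmHg.
- ETCO2: 35-40 mmHg.
- In both arms, ETCO2 guides care continuously, and PaCO2 governs whenever an arterial sample is taken.

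The clinical team should confirm the values. Using the same rule in both arms avoids adding a difference in care between them. The governing sentence also covers a patient whose gap proves larger than 5 mmHg when a sample happens to be taken.

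The cost is two edited lines and one added sentence. No sampling schedule or new access is required, since an arterial line is already planned for every patient. The downside is an ETCO2 target 5 mmHg wide instead of 10.
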